- m* It is strongly recommended that participants have documented evidence of protective immunity to tetanus and have completed tetanus vaccination series (with booster if needed) per local guidelines 14 days prior to Baseline (Visit 2). This recommendation applies to any other age and gender-specific appropriate non-live vaccination series as per local guidelines as well. If live vaccines are required as per local guidelines, these must be completed 12 weeks prior to Baseline.
- n* Assessments may be repeated for confirmation if deemed medically necessary.
- o* QuantiFERON TB gold test should be collected for all participants at the Screening (Visit 1). If the result is confirmed positive, the participant should be referred to an Infectious Disease specialist.
- p* FSH only if needed to confirm post-menopausal status during Screening.
- q* COVID-19 molecular test (if COVID-19 testing is required per local guidelines to be determined for each site). It is strongly recommended that participants have completed required COVID-19 vaccination series (with booster[s]), inactivated influenza vaccination, and pneumococcal vaccination per local guidelines 14 days prior to Baseline (Visit 2). This recommendation applies to any other age and gender-specific appropriate non-live vaccination series as per local guidelines as well. If live vaccines are required as per local guidelines, these must be completed 12 weeks prior to Baseline.
- r* Please refer to [Table 4](#) – Prohibited therapy prior to Baseline for detailed description of required washout periods for various medications.
- s* Daily diary is used for daily recording of [REDACTED], participant daily analgesic use, and [REDACTED] from at minimum 4 days prior to Baseline (Visit 2) to Week 28 (Visit 16). It should preferably be completed at about the same time every evening. It may also be used to document IMP administration if the participant receives IMP through home nursing.
- t* Diary for IMP administration must be completed to document IMP administration if participant receives IMP through home nursing.
- u* Sites are encouraged to contact participants 10 days prior to Baseline (Visit 2) to confirm compliance with daily pain collection and daily analgesic use in the daily diary.
- v* All eligible participants will be treated for 28 weeks, receiving a SC administration of IMP or placebo every 2 weeks for the first 14 weeks based on randomization, and then starting at Week 16 (Visit 10) all participants will receive IMP every 2 weeks until the last dose is administered at Week 26 (Visit 15).
- w* Per Investigator discretion, participants may resume treatment for HS as needed (including, but not limited to oral and topical antibiotics, corticosteroids, opioid and non-opioid analgesics, spironolactone, finasteride, or metformin). Participants may also receive unlimited lesion intervention as needed per Investigator discretion.
- x* Vital signs, including body temperature (°C), heart rate (beats per minute), respiratory rate (breaths per minute), and systolic and diastolic blood pressure (mm Hg), will be measured at all visits detailed in the flowchart.
- y* Physical examination will include examination of skin, nasal cavities, eyes, ears, cardiovascular, respiratory, gastrointestinal, neurological, lymphatic, and musculoskeletal systems. A brief symptom-directed physical examination should be performed at other visits if, in the opinion of the Investigator, it is warranted by the participant's AE status or on review of symptoms and will include, at a minimum, assessments of the skin, cardiovascular system, and abdomen (liver and spleen). Height will be measured and recorded at the Screening Visit. Weight will also be measured and recorded at the Screening, Baseline, Week 16, and EOS Visit.
- z* For fasting lipid panel, participant must be fasting for 8 hours prior to laboratory testing (may consume water). If unable to fast, participant may consume a light meal. Labs drawn during non-fasting laboratory testing will include hematology and clinical chemistry only. For laboratory testing please see [Table 12](#).
- aa* Only for WOCBP: serum pregnancy test at Screening (Visit 1) and urine pregnancy tests at every visit from Baseline (Visit 2) to EOS (Visit 17). A negative result must be obtained at Screening (Visit 1) and at Baseline (Visit 2) prior to randomization. In case of positive urine test, the study treatment will be withheld and a serum pregnancy test to confirm the pregnancy should be performed as soon as possible. Pregnancy will lead to definitive treatment discontinuation in all cases.

*bb* Hidradenitis Suppurativa Clinical Parameters will be performed at each designated study visit and must address all relevant anatomical regions in each participant; the number, location, longest distance between relevant lesions, and whether the lesions are separated by normal-appearing skin will be measured in each anatomical area ; Hurley Stage is included as an assessment performed during the HS clinical parameters; Hidradenitis Suppurativa Physician's Global Assessment is included as an assessment performed during the HS clinical parameters. The site is responsible for counting lesions that received intervention as permanently present in the lesion counts from the date of the intervention. The data collected from the HS clinical parameters will be used for the derivation of the HiSCR50, HiSCR75, HiSCR90, IHS4, AN count, Hidradenitis Suppurative Physician's Global Assessment, raw counts, and disease flares. For each participant it is recommended that the HS Clinical Parameters is assessed by the same Investigator during the entire study if possible.

*cc* Investigator review of participant daily analgesic use diary.

*dd* The participant should complete the questionnaire before site personnel perform any clinic assessments and before any interaction with the site personnel has occurred to avoid biasing the participant's response.

*ee* Number of samples (tubes) and quantity of biological samples needed for each assessment can be found in the laboratory manual.

*ff* Up to 4 hours prior to IMP administration.

*gg* PD biomarkers will include serum TNF and serum OX40L.

*hh* Optional assessment with skin biopsies at Baseline (Visit 2) and Week 16 (Visit 10) will be performed. Participants without history of hypertrophic or keloid scarring as assessed by the Investigator through participant interview and review of medical history can choose whether they would like to participate in optional assessment. If they consent to participate, the participants will have one lesional biopsy of an inflammatory nodule and one non-lesional biopsy at Baseline (Visit 2) and Week 16 (Visit 10) (for a total of 4 biopsies). Biopsy is to be performed after HS clinical parameters, but before IMP administration at study visit. Sutures may be placed per the discretion of the Investigator. Participants will be scheduled for an additional visit 1 week after skin biopsy for suture removal if sutures are placed per the discretion of the Investigator. Sample will be processed per instructions in the laboratory manual.

*ii* Biomarker panel will include, but is not limited to, CRP, hs-CRP, , SAA, and ANC. Hematology sample will be drawn for neutrophils (with other values reported per laboratory manual).

*jj* Optional sample collected for potential retrospective safety follow-up and/or additional exploratory analysis.

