 [REDACTED] FSH=follicle stimulating hormone; HBsAg=hepatitis B surface antigen; HBV=hepatitis B virus; HCV-Ab=hepatitis C virus antibody; HS=hidradenitis suppurativa clinical response; HIV=human immunodeficiency virus; HS=hidradenitis suppurativa; [REDACTED] hs-CRP=high-sensitivity C-reactive protein; IgG=immunoglobulin G; IgM anti-HBc=immunoglobulin M antibody to hepatitis B core antigen; IHS4=International Hidradenitis Suppurativa Severity Score System; IMP=Investigational Medicinal Product; IRT=interactive response technology; OX40L=OX40-Ligand; PD=pharmacodynamic(s); PK=pharmacokinetic(s); [REDACTED]; SAA=serum amyloid A; SAE=serious adverse event; SC=subcutaneous(ly); TB=tuberculosis; [REDACTED]  
 | V=visit; W=week; WOCBP=women of childbearing potential.

- a When several assessments take place at the same time, the following order should be respected: questionnaires, ECG, followed by vital signs, AE reporting, prior and concomitant medications, daily diary review, blood sampling, physical examination, lesion intervention if needed, HS clinical parameters, skin biopsy, and IMP administration.
- b A maximum of 28 days is required depending on participants' prior and concomitant medications. Randomization of the participant must take these constraints into consideration.
- c All visits are done on-site except if home nursing is arranged for visits at Week 18, 22, or 26. Participants in Denmark will not have home nursing, please refer to [Section 10.8.1.2](#).
- d Participants who discontinue IMP treatment prior to completing the 28-week treatment period and 8-week Follow-up Period will be evaluated as soon as possible at the individual participant's EOT Visit, using procedures as planned for the EOT Visit at Week 28 (Visit 16). At their EOT Visit, participants will resume their HS medications or other appropriate therapy as needed per Investigator discretion after the EOT study assessments have been performed and will enter the 8-week safety Follow-up Period, concluding with EOS Visit (Visit 17).
- e The study visits occur on the planned dates (relative to the first IMP), as scheduled.
- f Visits at Week 18, 22, and 26 may be performed with a home nursing service.
- g To qualify for randomization all inclusion criteria and none of the exclusion criteria are met by the participant.
- h Update inclusion/exclusion criteria, medical and surgical history, and prior and concomitant medications information to assure participant eligibility.

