AE=adverse event; Ab=antibody; AN=abscess and inflammatory nodule; ANC=absolute neutrophil count; anti-HBc=hepatitis B core antibody; anti-HBs=hepatitis B surface antibody; COVID-19=coronavirus disease 2019; CRP=C-reactive protein; C-SSRS= Columbia-Suicide Severity Rating Scale; D=day; ECG=electrocardiogram; eCRF=electronic case report form; EOT=end of treatment; EOS=end of study; [REDACTED] FSH=follicle stimulating hormone; HBsAg=hepatitis B surface antigen; HBV=hepatitis B virus; HCV-Ab=hepatitis C virus antibody; HS=hidradenitis suppurativa clinical response; HIV=human immunodeficiency virus; HS=hidradenitis suppurativa; [REDACTED]; hs-CRP=high-sensitivity C-reactive protein; IgG=immunoglobulin G; IgM anti-HBc=immunoglobulin M antibody to hepatitis B core antigen; IHS4=International Hidradenitis Suppurativa Severity Score System; IMP=Investigational Medicinal Product; IRT=interactive response technology; OX40L=OX40-Ligand; PD=pharmacodynamic(s); PK=pharmacokinetic(s); [REDACTED]; SAA=serum amyloid A; SAE=serious adverse event; SC=subcutaneous(ly); TB=tuberculosis; [REDACTED] V=visit; W=week; WOCBP=women of childbearing potential.

a All participants in the US will be assessed for response at the Week 20 visit based on the HS Clinical Parameters. Response will be defined as ≥50% reduction from Baseline in the total AN count, with no increase from Baseline in abscess or draining tunnel count at Week 20. For non-responders, they will not continue in Period B and immediately begin procedures for the EOT visit as depicted in the SOA. For responders, they will continue in Period B and perform assessments for the Week 20 visit as depicted in the SOA.

- b* At the Week 20 visit, HS Clinical Parameters will be performed prior to any assessment to assess treatment response. At all other visits, when several assessments take place at the same time, the following order should be respected: questionnaires, ECG, followed by vital signs, AE reporting, prior and concomitant medications, daily diary review, blood sampling, physical examination, lesion intervention if needed, HS clinical parameters, skin biopsy, and IMP administration.
- c* A maximum of 28 days is required depending on participants' prior and concomitant medications. Randomization of the participant must take these constraints into consideration.
- d* All visits are done on-site except if home nursing is arranged for visits at Week 18, 22, or 26.

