### **Lesion Intervention**

In the event that an acutely painful lesion occurs that requires an immediate intervention, Investigators will have the option to perform protocol-allowed interventions.

Only 2 types of interventions are allowed: injection with intralesional triamcinolone acetonide suspension (at a concentration of up to 10 mg/mL, up to 1 mL) and I&D.

For participants in Chile, intralesional betamethasone (at a maximum dose of up to 1.5 mg, diluted in sterile normal saline per Investigator discretion) may be substituted for intralesional triamcinolone.

New systemic and topical therapies following I&D (including antibiotics), are prohibited.

Participants should continue using any ongoing oral and topical therapies (with the constraints as described in [Section 6.9.1](#)) during the study. Concomitant medications associated with the lesion intervention(s) must be captured in the source and on the appropriate eCRF.

Protocol-allowed interventions are prohibited during Period A for all participants except those in Australia. For participants in Australia, 2 lesion interventions are allowed during Period A. An intervention can occur on two different lesions at the same visit or on the same lesion at two different study visits.

During Period B, maximally two interventions every 4 weeks are permitted. An intervention can occur on two different lesions at the same visit or on the same lesion at two different study visits.

All study visit assessments must occur before any interventions are performed. The site will be required to count any lesion that undergoes an intervention as permanently present from the date of the intervention and must account for it in the source document(s) and on the appropriate eCRF.

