## 8 STUDY ASSESSMENTS AND PROCEDURES

- Study procedures and their timing are summarized in the SoA. Protocol waivers or exemptions are not allowed.
- Adherence to the study design requirements, including those specified in the SoA, is essential and required for study conduct.
- All screening evaluations must be completed and reviewed to confirm that potential participants meet all eligibility criteria. The Investigator will maintain a screening log to record details of all participants screened and to confirm eligibility or record reasons for screening failure, as applicable.
- Procedures conducted as part of the participant's routine clinical management (eg, blood count, urine tests) and obtained before signing of the ICF may be utilized for Screening or Baseline purposes provided the procedures met the protocol-specified criteria and were performed within the timeframe defined in the SoA.
- In the event of a significant study-continuity issue (eg, caused by a pandemic), alternate strategies for participant visits, assessments, medication distribution and monitoring may be implemented by the Sponsor or the Investigator, as per local Health Authority/ethics requirements (see Appendix 9 [[Section 10.9](#)]).
- Safety/laboratory results that could unblind the study will not be reported to investigative sites or other blinded personnel until the study has been unblinded.

For a regional or national emergency declared by a governmental agency, contingency measures are included in Appendix 9 ([Section 10.9](#): Contingency measures for a regional or national emergency that is declared by a governmental agency).

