The post-treatment period is defined as the period after the end of the TE period of Period B, or after the end of TE period of Period A if the participant does not enter the Period B.

Any lesion that is treated with steroid injection, deroofing, or other local intervention, the lesion is considered present throughout the double-blind period and open-label period. Types of lesions include abscess, non-inflammatory nodule, inflammatory nodule, nondraining tunnel, draining tunnel, hypertrophic scar.

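### The visit-order footnotes in both Schedules of Activities put lesion intervention before the HS lesion count, while Protocol Section 6.9.2 requires the count first

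*Protocol*

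**What the plan says.** Protocol Section 1.3.1, footnote a, says what order should be kept when several procedures fall at the same visit. The end of the list reads "blood sampling, physical examination, lesion intervention if needed, HS clinical parameters, skin biopsy, and IMP administration". Footnote b of Section 1.3.2 gives US participants the same sequence, "physical examination, lesion intervention if needed, HS clinical parameters, skin biopsy, and IMP administration", with one exception: "At the Week 20 visit, HS Clinical Parameters will be performed prior to any assessment to assess treatment response".

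Section 6.9.2, under Lesion Intervention, states: "All study visit assessments must occur before any interventions are performed". Section 8 adds a general rule: "Adherence to the study design requirements, including those specified in the SoA, is essential and required for study conduct".

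The plan also says how treated lesions are counted. Footnote bb of Section 1.3.1 reads "The site is responsible for counting lesions that received intervention as permanently present in the lesion counts from the date of the intervention"; footnote cc of Section 1.3.2 and Section 6.9.2 say the same in substance. SAP Section 2.1 says of a treated lesion that "the lesion is considered present throughout the double-blind period and open-label period", and then lists the lesion types.

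On who may be treated, Section 6.9.2 bars interventions in Period A except in Australia, where two are allowed. It allows at most two every 4 weeks in Period B. At the EOT visit, footnote w (1.3.1) and footnote x (1.3.2) allow lesion intervention without limit.

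**The concern.** HiSCR50, HiSCR75, HiSCR90, IHS4, HS-PGA and flare are all derived from the HS Clinical Parameters. Most of these depend on lesion type as well as number. HiSCR50 fails if the abscess or draining tunnel count rises (Section 8.2.1.2). IHS4 gives each type its own coefficient (8.2.1.3), and HS-PGA separates abscesses and draining fistulas from nodules (8.2.1.6).

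Section 8.2.1.1 defines the types by signs the assessor can see or feel: an abscess by a collection of pus with signs such as fluctuance, a draining tunnel by its drainage. Incision and drainage can alter exactly those signs. A site that runs the visit from the SoA would treat first and classify afterwards; a site that works from Section 6.9.2 would classify first. The plan should not leave that to the site.

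**Working it through.** No arithmetic applies. The check compares the texts.

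1. *Is the lesion count covered by Section 6.9.2?* Yes. HS Clinical Parameters stand in the Efficacy block of both schedules and are described as an assessment in Section 8.2.1.1. A rule covering all study visit assessments therefore includes them.

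2. *Do the orders conflict?* Footnotes a and b: intervention, then count. Section 6.9.2: all assessments including the count, then intervention. These are opposite. All three are operative text, not amendment history, and nothing reconciles them. At US Week 20 the count comes first, so there is no conflict there.

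3. *Which text should give way?* The footnotes use *should* in a general list of procedures. Section 6.9.2 uses *must* in the section devoted to lesion intervention. The specific, mandatory text is the better guide to intent. Footnote d of Section 1.3.1 points the same way by placing other therapy "after the EOT study assessments have been performed". That support is thin, because it concerns participants who stop IMP early and does not mention lesion intervention.

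4. *What does the counting rule already protect?* A treated lesion is present from the date of the intervention, which covers a count taken later at the same visit. Its presence is secured in either order. Its type is not expressly secured. The SAP's list of types follows directly on the rule, so the natural reading is that a treated abscess stays an abscess, but no sentence says so.

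5. *Where can it occur?* Only when a permitted intervention falls on a counting day.
- Period A outside Australia: no permitted exposure. Table 8 also keeps the associated local anesthetic prohibited until the Week 16 visit is complete.
- Period A in Australia: at most 2 interventions per participant, with post-Baseline counts at Weeks 2, 4, 8, 12 and 16 (Section 1.3.1).
- Period B: counts at Week 20 (non-US only) and Week 24. The US schedule appears also to mark Week 18, a visit that may be done by home nursing; if that is intended, it joins this list.
- Week 28/EOT: a count is scheduled and intervention is unlimited. US non-responders have their EOT visit at Week 20, where the count already comes first.

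SAP Section 2.5 makes the Period B efficacy analyses descriptive.

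**The case against.** The strongest reply is that a careful site already knows what to do: *must* outranks *should*, and Section 6.9.2 is the specific rule. That stands, and it settles which text to change. It does not remove the conflict, because the footnote is where staff look for the order of a visit.

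A reader might infer from Section 8 that both texts bind equally, so that a site breaches the protocol whichever it follows. The documents do not support so strong a reading. Section 8 is a general sentence about adherence, and the footnote it would enforce is itself worded as *should*.

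The second reply is that the counts are already protected. The permanently-present rule applies on the day of treatment, Section 6.9.2 requires the treated lesion to be accounted for in source and eCRF, and in the footnote order a physical examination that includes the skin comes before the intervention. This stands for presence, and probably for type on the natural reading. The skin examination is a weaker safeguard: it is not a typed lesion count, and Section 1.3.1 does not schedule it at Week 2.

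The third reply is that the primary endpoint is barely exposed. That stands too.

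**Conclusion.** Wrong as written, and minor. The two footnotes contradict Section 6.9.2 and should be brought into line with it. What remains at risk is the recorded type of a lesion drained or injected earlier at the same visit.

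A reader might go further and infer that Week 16 HiSCR50 is biased. The documents do not show that. Outside Australia, no permitted intervention can precede the Week 16 count. Within Australia, the cap is two per participant, the number of participants is not given, and the number treated on a counting day may be zero. Even then, the natural reading of the counting rule keeps the lesion's type. In Period B and at EOT the conflict reaches more participants, but the efficacy analyses there are descriptive.

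This rests on two assumptions: that interventions stay within what the protocol permits, and that sites apply the permanently-present rule. The size of any effect cannot be calculated from the documents.

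**What to change.** In footnote a of Section 1.3.1 and footnote b of Section 1.3.2, move the lesion-intervention item to after HS Clinical Parameters. On biopsy days (Baseline and Week 16) it should also follow the skin biopsy, which footnotes hh and ii describe as an assessment. The US Week 20 exception can stay as it is. Tell sites by a short memo.

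Optionally, add one sentence to Section 6.9.2 and SAP Section 2.1 saying that a treated lesion stays in the counts under its pre-intervention type. This makes the natural reading explicit but is not needed to resolve the ordering conflict.

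The cost is one phrase moved in two footnotes, plus the memo. No visit or procedure is added, and the rules on which interventions are allowed, and when, do not change.
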